## **Appendix E – Medications That May Cause QTc Prolongation**

The following table presents a list of drugs that may prolong the QTc. These drugs are prohibited during the study. Romidepsin may be administered after a 5 half-life washout period elapses following the use of these drugs. Washout period is based on roughly 5 half-lives and rounded to a convenient interval. Patients taking lower risk drugs not known to interact with the study drug will be monitored and may be allowed on study.

## **Medications That May Cause QTc Prolongation**

Compound (Brand Name)	Compound Half-Life	Possible Washout Period (Hours)	Possible Washout Period (Days)
Antiarrhythmics		,	1
Amiodarone (Cordarone, Pacerone)	58 days (15-142) 36 days (active metabolite)		180
Disopyramide (Norpace, Norpace CR)	6.7 hr (4-10)	36	
Dofetilide (Tikosyn)	10 hr	48	
Flecainide (Tambocor)	20 hr (12-27)		5
Ibutilide (Corvert)	6 hr (2-12) (variable among patients)	36	
Procainamide (Pronestyl, Procanbid,	3-4 hr for PA and NAPA (active	24	
Procan)	metabolite)		
Quinidine (Quinaglute, Cardioquin, Quinidex)	6-8 hr in adult; 3-4 hr in children	36	
Sotalol (Betapace, Sorine)	12 hr	72	
Antibiotics			
Azithromycin (Zithromax, Zithromax Tri- Pack, Zithromax Z-Pak, Zmax)	Immediate release: 68-72 hr, extended release 59 hr		12-15
Clarithromycin (Biaxin, Biaxin XL)	Nonlinear PK 3-4 hr (250 mg Q12) 5-7 hr (500 mg Q12)	36	
Erythromycin (Benzamycin, Eyrc, Eglades, Erygel, E-solve 2, Akne-Mycin, Eryderm, Sansac, Erythro-Statin, Erymax, Staticin, T-Stat, C-solve-2, Erycetter, PCE, Ery-Tab, E-Mycin, E-Base, E.E.S., Eryped, E.E.S 200, E.E.S 400, Pediamycin, Eryzole, Erythrocin)			
Gatifloxacin (Tequin, Tequin Teqpaq)	7-14 hr	48	
Grepafloxacin (Raxar) Antibiotics (cont'd)	16 hr		3
Levofloxacin (Levaquin, Quixin, Elequin)	6-8 hr	48	
Moxifloxacin (Avelox, Vigamox)	12 ± 1.3 hr	72	
Sparfloxacin (Zagam)	20 hr (16-30)		4
Telithromycin (Ketex)	2-3 hr	24	
Anticonvulsants			
Felbamate (Felbatol)	20-23 hr		5
Fosphenytoin (Cerebyx)	12-29 hr		6
Antidepressants			•
Venlafaxine (Effexor)	5 ± 2 hr for parent comp. 11± 2 hr for OVD (active metabolite)	60	
Antidiarrheals			
Octreotide (Sandostatin)	1.7 hr	12	
Antiemetics			•
Dolasetron (Anzemet)	8.1 hr		
Droperidol (Inapsin)	2.2 hr	10	
Domperidone (Motilium)	7-8 hr	48	
Palonosetron (Aloxi) Antihypertensives	40 hr	 	10

Compound (Brand Name)	Compound Half-Life	Possible Washout Period (Hours)	Possible Washout Period (Days)
Moexipril/Hydrochlorothiazide (Uniretic)	2-9 hr(include active metabolite) for moexipril; 5.6-14.8 hr for HCTZ	48	
Antimalarials			•
Halofantrine (Halfan)	6-10 days (variable among individuals)		45
Quinidine (Quinaglute, Cardioquin, Quinidex)	6-8 hr in adult; 3-4 hr in children	36	
Antimanics			
Lithium (Eskalith, Lithobid, Lithonate)	24 hr (10-50)		7
Antineoplastics			
Arsenic trioxide (Trisenox)	Not characterized		
Tamoxifen (Nolvadex)	5-7 days (biphasic)		30
Antiprotozoals			
Pentamidine (NebuPent, Pentam)	6.4 ± 1.3 hr	36	
Antipsychotic agents			
Chlorpromazine (Thorazine)	30 ± 7 hr		7
Haloperidol (Haldol)	18 ± 5 hr		5
Mesoridazine (Serentil)	24-48 hr (animal study)		10
Pimozide (Orap)	55 hr		14
(Continued from previous page)			
Antipsychotic agents (cont'd)			
Quetiapine (Seroquel)	6 hr	36	
Risperidone (Risperdal, Risperdal Consta)	3-20 hr (extensive to poor metabolizer) 9-hydroxyrisperidone (active metabolite) T 1/2 = 21-30 hr (extensive to poor metabolizer)		4
Thioridazine (Mellaril)	20-40 hr (Phenothiazines)		7
Ziprasidone (Geodon, Zeldox)	7 hr	36	
Antispastics			
Tizanidine (Zanaflex)	2.5 hr	12	
Antivirals	-		
Amantadine (Symadine, Symmetrel)	17 ± hr (10-25)		4
Foscarnet (Foscavir)	87.5 ± 41.8 hr (distribution and release from bone)		20
Analgesics			
Levomethadyl (Orlaam)	Multiple compartment PK with active metabolite 2.6 day for LAAM, 2 day for nor-LAAM, 4 day for dinor-LAAM		20
Asthma medications			
Salmeterol (Advair Diskus, Serevent, Serevent Diskus)	5.5 hr (only one datum)	36	
Calcium channel blockers			-
Bepridil (Vascor)	42 hr (26-64)		10
Isradipine (DynaCirc)	8 hr (multiple metabolites)	48	1

Compound (Brand Name)	Possible Washout Period (Hours)	Possible Washout Period (Days)	
Nicardipine (Cardene) Cholinergic enhancers	~2 hr post IV infusion	12	
Cisapride (Propulsid)  Diuretics	6-12 hr, up to 20 hr	60	
Indapamide (Lozol) Immunosuppressants	14 hr (biphasic elimination)		3
Tacrolimus (Prograf, Protopic)  Migraine medications	~34 hr in healthy patients ; ~19 hr in kidney transplant		7
Naratriptan (Amerge)	6 hr	36	1
Sumatriptan (Imitrex)	2.5 hr	12	
Zolmitriptan (Zomig)	2.8-3.7 hr (higher in female)	18	
Narcotic pain relievers	,	1	
Methadone (Dolophine, Methadose)	15-30 hr		7
Sedatives	1		
Chloral hydrate	Readily converted to Trichloroethanol (active metabolite T½= 7-10 hour)	48	

## Appendix F - Medications That May Inhibit CYP3A4

The following table presents a list of drugs that may inhibit CYP3A4. As romidepsin is predominately metabolized by CYP3A4, inhibition of this enzyme could result in elevated plasma levels or increased exposure to romidepsin. Romidepsin may be administered after a 5 half-life washout period elapses following the use of these drugs. Washout period is based on roughly 5 half-lives and rounded to a convenient interval.

Medications That May Inhibit CYP3A4

Medications That May Inhibit CYP3A4  Compound (Brand Names)	Compound Half-Life	Possible Washout Period Hours	Possible Washout -Period Days
Azole Antifungals	Į	li loui 3	Day3
Clotrimazole (Mycelex, Lotrimin, Lotrisone)	Not available		
Ketoconazole (Nizoral, Ketozole)	6 hr (2-8 hr)	30 hr	
Itraconazole (Sporanox)	21 hr		5 days
Fluconazole (Diflucan)	3 hr	15 hr	
Miconazole (Monistat) HIV Protease Inhibitors	57 hr	1	11 days
Ritonavir (Norvir, Kaletra)	4 hr	20 hr	
Indinavir (Crixivan)	2 hr	10 hr	
Saquinavir (Invirase, Fortovase)	5 hr	25 hr	
Nelfinavir (Viracept)	4 hr	20 hr	
Delavirdine (Rescriptor)	6 hr	30 hr	
Macrolide Antibiotics			
Troleandomycin (Tao)	Not available	10 hr	
solve 2, Akne-Mycin, Eryderm, Sansac, Erythro-Statin, Erymax, Staticin, T-Stat, C-solve-2, Erycetter, PCE, Ery-Tab, E-Mycin, E-Base, E.E.S., Eryped, E.E.S. 200, E.E.S. 400, Pediamycin, Eryzole, Erythrocin)			
Clarithromycin (Prevpac, Biaxin)	5 hr	25 hr	
Other Antibiotics			
Chloramphenicol (Chloromycetin, Chloroptic)	4 hr	20 hr	
Ciprofloxacin (Ciprodex, Cipro, Ciloxan)	4 hr	20 hr	
Norfloxacin (Noroxin, Chibroxin) Serotonin Reuptake Inhibitors (SSRI's)	4 hr	20 hr	 
Fluoxetine (Prozac, Sarafem, Symbyax)	Fluoxetine 5 days Norfluoxetine (active metabolite) 12 days (4- 16 days)	45 h	60 days
Nefazodone (Serzone)	3 hr	15 hr	
Fluvoxamine (Luvox) Antiemetics	16 hr	 	3 days
Aprepitant (Emend)	11 hr (9-13 hr)		2 days

Compound (Brand Names)	Compound Half-Life	Possible Washout Period Hours	Possible Washout Period Days
Oral Contraceptives			
Ethinyl-estradiol (Kariva, Velivet, Mircette, Desogen, Cyclessa, Ortho-Cept, Yasmin, Demulen, Zovia, NuvaRing, Seasonale, Lessina, Portia, Levlite, Nordette, Aviane, Enpresse, Trivora, Levora, Alesse, Triphasil, Ortho Evra, Ovcon, Nortrel, Gencept, Balziva, Brevicon, Norinyl, Norethin, Aranelle, Ortho-Novum, Modicon, Tri-Norinyl, Femhrt, Junel, Loestrin, Estrostep, Microgestin, Tri-Previfem, Previfem, Tri-Sprintec, Sprintec, Ortho Tri-Cyclen, Cryselle, Lowogestrel, Ogestrel, Lo/Ovral, Ovral)			3 days
Oral Contraceptives (cont'd)			
Mifepristone (Mifeprex, RU-486)	18 hr		4 days
Gestodene Histamine H2-Receptor Antagonists	20-22 hr	l	5 days
Cimetidine (Tagamet) Antiarrhythmic Drugs	2 hr	10 hr	
Quinidine (Quinaglute, Cardioquin, Quinidex)	7 hr	35 hr	
Amiodarone (Cordarone, Pacerone)	53 days (15-142 days)		265 days
Antihypertensives			
Diltiazem (Taztia, Cartia, Cardizem, Dilt-CD, Dilacor, Teczem, Tiamate. Trizac)	3 hr [7 hr for extended release (Trizac)]	35 hrs	
Verapamil (Tarka, Verelan, Isoptin, Covera-HS, Calan)	8 hr	40 hr	
Calcium Channel Blocker	•		
Mibefradil (Posicor)  Others	21 hr (17-25 hr)		5 days
	Not oveilable	Ī	1
Grapefruit juice Star fruit	Not available		
Stat Ituil	Not available		l

## Appendix G - Study Calendar

		1 1	_							_			_	_	
Tabl	е	6:	S	tudy	Eva	lua	ıti	OI	n	S	che	90	lul	е	

		Cycle 1 Cycle				le 2 a	End of study		
Procedure	Screening	Day 1	Day 8	Day 15	Day 1	Day 8	Day 15	End of cycle	
Record prior medications, treatments	Х								
Record prior anti-cancer therapies	Х								
Physical examination 	Х	Х	Х	x 	Х				Х
ECOG performance status 	X	Х			Х				Х
12 Lead ECG 	X	Х	Х		Х	Х			
ECHO or cardiac MRI	Х								
Hematology	X	Х	Х	X 	X 	X 			Х
LDH 	X				X 				
Electolytes 	X	Х	Х	X 	X 	X 			Х
Liver function analysis 	X	Х	Х	X 	X 				Х
Pregnancy testing 	X	Х	Х	X 	X 				Х
REMS™ program (patient enrollment)	X								
Start lenalidomide 		Х			х				
Carfilzomib*		Х	Х		Х	Х			
Romidepsin*		Х	Х		Х	Х			
Disease/Response assessment 	Х							X 	x 
Record adverse events 		Х	Х	X 	Х	Х	X 		Х
Record concomitant medications	Х	Х	Х	X 	Х	Х	X 		Х

Table 7 Legend

\* For cycle 1, study assessments and/or romidepsin and carfilzomib dosing may be delayed a) up to 3 days in the setting of grade 3 thrombocytopenia or neutropenia that recovers or b) up to 1 day for other scheduling considerations.

For cycle 1, labs may be performed up to 1 day prior to treatment. After completion of cycle 1, labs may be performed up to 3 days prior to treatment. For cycle 2 and beyond, romidepsin and carfilzomib dosing may be delayed up to 3 days or given up to one day ahead of the scheduled dosing. Romidepsin doses must be given at least 6 days apart.

Memorial Sloan Kettering Cancer Center IRB Number: 14-179 A(6) Approval date: 12-Dec-2017

Administrative Update 1:06-Dec-2018

If Physical examination, vital signs, weight and ECOG performance status were done within 7 days of Day 1, they do not need to be repeated at study cycle X, Day 1 (excluding cycle 1 in the phase lb portion). An unscheduled visit can occur at any time during the study.

The schedule for ECG monitoring is found in section 10.5 and romidepsin dose modifications in Table 5. After cycle 2 the schedule can be amended as clinically indicated in section 10.5.

Sodium, potassium, chloride, bicarbonate, BUN, creatinine, calcium, and glucose are part of the electrolyte assessment at every time point. Magnesium will be added to the electrolyte panel at screening, days 1, and 8 of the treatment cycle, and at the end of study visit. Liver function analysis (at least total protein, albumin, AST, ALT, alkaline phosphatase, total bilirubin) is necessary on day 1 of each cycle but does not have to be resulted to initiate treatment. Liver function analysis must be resulted within 7 days of cycle 1 day 1 and cycle 2 day 1 to proceed with treatment. Liver function analysis must be resulted within 14 days of day 1 of cycle 3 and beyond to proceed with treatment

Pregnancy tests for females of childbearing potential are required through the Revlimid REMS® program. A female of childbearing potential (FCBP) is a sexually mature female who: 1) has not undergone a hysterectomy or bilateral oophorectomy; or 2) has not been naturally postmenopausal for at least 24 consecutive months (i.e., has had menses at any time in the preceding 24 consecutive months). Pregnancy tests must occur within 10 - 14 days and again within 24 hours prior to prescribing lenalidomide for Cycle 1 (prescriptions must be filled within 7 days). FCBP with regular or no menstruation must have a pregnancy test weekly for the first 28 days and then every 28 days while on therapy (including breaks in therapy); at discontinuation of lenalidomide and at Day 28 post the last dose of lenalidomide. Females with irregular menstruation must have a pregnancy test weekly for the first 28 days and then every 14 days while on therapy (including breaks in therapy), at discontinuation of lenalidomide and at Day 14 and Day 28 post the last dose of lenalidomide (see Appendix C: Risks of Fetal Exposure, Pregnancy Testing Guidelines and Acceptable Birth Control Methods).

Lenalidomide must be prescribed through and in compliance with the **REMS™** program of Celgene Corporation. Prescriptions must be filled within 7 days. Consideration should be given to prescribing lenalidomide 5 to 7 days in advance of Day 1 of each cycle to allow time for required patient and prescriber surveys, and drug shipment to patient. Any unused Revlimid® (lenalidomide) should be returned to Biologics for disposal in accordance with the **REMS™** program.

Baseline disease assessments must be performed after discontinuation of most recent anti-cancer therapy including systemic steroids. Outside scans are acceptable if performed within 28 days.

 The imaging modality for evaluation will be dependent on disease subtype. For aggressi ve lymphomas (e.g. DLBCL, PTCL, HL), PET/CT will be used for evaluation of response. For indolent lymphomas, CT alone or PET/CT may be used at the discretion of the treating physician. A bone marrow will only be repeated to confirm a complete response if previously known to be involved. Cutaneous T-cell lymphoma patients (CTCL) will have an mSWAT (Appendix D) performed at these time points and imaging at baseline. In CTCL patient's, imaging will be repeated if appropriate (patients with known nodal or visceral disease) every other cycle. Sezary panel in patients with Sezary syndrome. Cutaneous lymphoma patients without nodal or visceral disease will have imaging repeated only to confirm a complete response.

 An additional safety assessment will be done 28 days (+/- 7 days) following the last dose of protocol therapy.

Response assessment will be performed at the end of cycles 2. Thereafter, response assessment will occur at the end of every third cycle (5.8,11, etc..) until disease progression or removal from study.

10 +/- 3 days

if not performed within 28 days

For cycle 3 and beyond, laboratory assessments performed up to three days prior to the day of treatment are adequate for treatment as long as they are within the treatment parameters.

 For cycles 2, 3 and 4, concomitant medications and adverse events may be performed via an assessment by telephone +/- 3 days of day 15 of the cycle. Beyond cycle 4, day 15 assessments are not required.  5 days to + 3 days.

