#### 8.1 PRETREATMENT EVALUATION

# 8.2 Documentation of tests resulted and/or verification to be performed within 28 days of starting treatment.

- 1. Record prior medications and treatments
- 2. Record prior anti-cancer therapy
- 3. Physical examination
- 4. ECOG performance status
- 5. 12 lead ECG
- 6. ECHO or Cardiac MRI
- 7. Complete metabolic panel, including magnesium and phosphorus
- 8. Lactate dehydrogenase (LDH)
- 9. PET/CT or CT Chest, Abdomen, and Pelvis
- 10. Register patient with Revlimid REMS® program.

- 11. mSWAT for patient with cutaneous lymphoma.
- 12. Sezary panel in patients with Sezary syndrome only.
  - Sezary panel: peripheral blood flow cytometry including CD2, CD3, CD4, CD8, CD26 and or CD7
- 13. Phase IIa only: patients with suspected or known prior bone marrow involvement must have a bone marrow biopsy performed.
- 14. Pregnancy testing for females of childbearing potential within 10-14 days and again 24 hours prior to prescribing lenalidomide per the Revlimid REMS® program.

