#### 9.3.2 Dose Escalation

Subjects enrolled into the phase 1b portion will enroll at dosing level 1 with three patients per dosing level (3+3 design). A cycle will be 21-days. Based on toxicity

and activity seen during the phase lb portion, additional dose levels and/or alternate 28 day cycle may be explored through an amendment. The carfilzomib will be given intravenously weekly on days 1 and 8. The romidepsin will be given intravenously on days 1 and 8. The lenalidomide will be given as a once a day oral drug given on days 1-14. It is preferred that romidepsin be administered prior to carfilzomib.

TABLE 1: Phase I Dose Escalation			
Dose	Romidepsin	Lenalidomide	Carfilzomib
Level			(mg/m²)
-1	8 mg/m 	10 mg	20
1	8 mg/m 	15 mg	36
2	8 mg/m 	15 mg	45
3	10 mg/m 	20 mg	45
4	10 mg/m 	20mg	56
		J	

If all three patients complete one cycle of therapy without a DLT at the respective

- dose level then the subsequent dose level can be accrued.

  A DLT is defined in cycle 1 of the phase I portion as:

   Non-hematologic toxicity of grade ≥3 (attributed to study drugs with the exception of alopecia, nausea, or grade ≥3 vomiting not responsive to antiemetics)
  - Hematologic grade 4 toxicity (attributed to study drugs) defined as grade 4 thrombocytopenia of any duration; grade 4 neutropenia lasting more than 5 days; or grade 4 anemia unexplained by the underlying disease
  - Grade ≥3 thrombocytopenia with clinically significant bleeding
  - Febrile neutropenia of any duration (ANC <1.0K/ µL with fever 38.5°C)
  - Inability to receive day 1 of cycle 2 due to continued drug-related toxicity including Grade ≥ 2 toxicity that does not resolve to Grade ≤ 1 by the start of the next cycle.
  - Grade 3 thrombocytopenia or neutropenia (attributed to study drug) within cycle 1 that results in a) ≥ 4 day delay in any romidepsin or carfilzomib dose or b) missing greater than 4 days of lenalidomide. (This criteria only applies to the **phase lb portion** and does not apply to the phase Ila stopping rules).

After the MTD is determined by either DLT or accrual of six patients without DLT at dose level 4 in the first cycle accrual to the phase Ib portion will be considered closed. The MTD from the phase lb study will be used for the phase lla portion.

Of note, only patients who complete ≥80% of the doses of carfilzomib, romidepsin and lenalidomide during the first cycle will be evaluable for MTD. Patients who do

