#### 9.5 **Dose Continuation, Modification and Interruption**

Subjects will be evaluated for AEs at each visit with the NCI CTCAE v4.0 used as a guide for the grading of severity. DLTs as defined will be tabulated in cycle 1 of phase Ib and cycles 1-4 of the phase Ila portion of the study. The toxicity decision rule for the Ila portion is described in Section 14.0. The sections below describe dose reduction steps, instructions for initiation of a new cycle of therapy and dose modifications during a cycle of therapy. Of note, if patient's experiences a greater than 10% change in body weight, dose of romidepsin should be adjusted accordingly. Doses do not need to be adjusted for less than 10% changes in body weight.

# 9.5.1 Instructions for Dose Modifications or Interruption During Phase 1 Cycle 1

There will be no dose reductions in cycle 1 phase 1. Inability to meet treatment criteria will result in holding the dose.

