## Side effects related to levels of substances found in the blood:

- Hyperbilirubinemia
- Hypokalemia
- Lymphopenia
- Hyponatremia
- Hypermagnesemia
- Increased creatinine
- Hypophosphatemia
- Elevated transaminases
- Elevated alkaline phosphatase

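### Phosphorus is measured at screening but in no scheduled on-treatment panel, so hypophosphatemia, a listed romidepsin effect that can meet the DLT definition, is not systematically ascertained

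*Combined protocol and SAP*

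**What the plan says.** Section 8.2 (tests within 28 days of starting treatment) asks for: "Complete metabolic panel, including magnesium and phosphorus". Section 11.0, under the less likely romidepsin effects on blood levels, lists "Hypophosphatemia".

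For the calendar's electrolyte row, Appendix G, footnote 3, states: "Sodium, potassium, chloride, bicarbonate, BUN, creatinine, calcium, and glucose are part of the electrolyte assessment at every time point". It continues: "Magnesium will be added to the electrolyte panel at screening, days 1, and 8 of the treatment cycle, and at the end of study visit". Its liver entry reads: "Liver function analysis (at least total protein, albumin, AST, ALT, alkaline phosphatase, total bilirubin) is necessary on day 1 of each cycle". Phosphorus appears in none of these.

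Section 9.3.2 includes among DLTs: "Non-hematologic toxicity of grade ≥3 (attributed to study drugs with the exception of alopecia, nausea, or grade ≥3 vomiting not responsive to antiemetics". Section 9.5 sets the windows: "DLTs as defined will be tabulated in cycle 1 of phase Ib and cycles 1-4 of the phase Ila portion of the study". Section 14.0 stops phase IIa for DLTs in 3 or more of the first 6 patients, 6 or more of the first 12, or more than 10 of 20.

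**The concern.** The plan takes a baseline value for a listed toxicity and schedules no on-drug value to compare with it. Characterizing safety by CTCAE v4.0 is the phase IIa primary endpoint, and DLT counts feed its only formal stopping rule. If testing is left to local habit, a report of no grade 3 hypophosphatemia could mean that it did not occur or that nobody measured it. Practice could also differ between the two recruiting centers named in Section 7.0, and the data would not show which explanation applies.

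**Working it through.** This is mainly a comparison of texts.

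**1. Where phosphorus is scheduled.**

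| Place | Tests named | Phosphorus? |
|---|---|---|
| Section 8.2, screening | Metabolic panel with magnesium and phosphorus | Yes |
| Appendix G footnote 3, electrolytes, every time point | Eight analytes | No |
| Footnote 3, addition | Magnesium | No |
| Footnote 3, liver panel | Six analytes as a minimum | No |
| Sections 10.2, 10.2.1 and 10.3, treatment parameters | ANC, platelets, potassium, magnesium, creatinine, AST/ALT | No |

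Footnote 3 does not name phosphorus at screening either, so it also differs from Section 8.2 there.

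**2. Is the omission typical of listed effects?** Section 11.0 gives romidepsin's blood-level effects in two lists: 7 likely and 9 less likely, 7 + 9 = 16.
- Hematology covers 4: thrombocytopenia, anemia, leukopenia and lymphopenia (assuming a differential count).
- The eight-analyte panel covers 5: glucose, calcium, potassium, sodium and creatinine.
- The added magnesium covers 2: low and high magnesium.
- The liver panel covers 4: albumin, bilirubin, transaminases and alkaline phosphatase.

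4 + 5 + 2 + 4 = 15. The sixteenth is hypophosphatemia.

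**3. Is footnote 3 a closed list?** It does not say so. However, the liver panel is expressly a minimum list while the electrolyte panel is not, and magnesium had to be added by name with its own days. The natural reading is that the eight analytes plus magnesium are the panel.

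**4. Would an event count?** Yes, if it is grade 3 or higher and attributed to study drugs. The stated exceptions concern alopecia, nausea and vomiting only. The one DLT criterion that Section 9.3.2 confines to phase Ib concerns platelets and neutrophils, so the non-hematologic criterion carries into phase IIa.

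**5. How sensitive is the stopping rule to unseen DLTs in general?** First, the plan's own figure. At a true rate of 30%, the first look stops with probability 1 - [0.7^6 + 6(0.3)(0.7^5) + 15(0.3^2)(0.7^4)] = 1 - (0.1176 + 0.3025 + 0.3241) = 0.256. Carrying the non-stopped paths to 12 and 20 patients gives 0.283 for the rule as written (more than 10 of 20). The printed value is 0.289, which a last boundary of 10 or more reproduces; that is a separate matter.

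If d percentage points of patients have a DLT that goes unseen and no other DLT, the rule behaves as if the rate were 30% - d:

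| Unseen points (assumed) | 0 | 1 | 3 | 5 | 10 |
|---|---|---|---|---|---|
| Stopping probability, rule as written | 0.283 | 0.261 | 0.220 | 0.183 | 0.104 |

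These values of d are assumptions. The documents give no hypophosphatemia rate and nothing to place it on this scale.

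**The case against.** A reader might infer that grade 3 hypophosphatemia cannot be found or counted, and that its reported rate must be zero. The documents do not support that. Nothing bars the test, and the calendar's footnote 1 allows unscheduled visits at any time. The adverse event reporting rules in Section 17.3.1 require abnormal laboratory results to be appraised, and clinically significant worsening in any laboratory parameter to be recorded. A value found that way would count if attributed to study drugs. But these rules act on results that exist; they order no test, so they leave ascertainment to chance.

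A grade 3 value is also not automatically a DLT, because attribution is required. This stands, and the conclusion is limited accordingly.

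Footnote 3 is silent on phosphorus at screening as well, where Section 8.2 does require it, so its silence does not prove that the test is not done. That is fair, but during treatment no other section supplies the requirement.

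The protocol does not test for every listed effect: hyperuricemia, among the rare romidepsin effects, has no named uric acid test, and the on-treatment chemistry in Section 10 follows values that gate dosing, which phosphorus does not. This keeps the point modest. Phosphorus differs in that the plan already collects its baseline.

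The listing of tumor lysis syndrome for the other two drugs might seem to strengthen the case. It does not: the gap concerns low phosphorus as a romidepsin effect, and the documents do not link the two.

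Finally, Section 9.3 records that the MTD is already set at dose level 1, so only phase IIa counts can still change.

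**Conclusion.** The point holds as a gap in ascertainment. No scheduled on-treatment panel names phosphorus, and hypophosphatemia is the one effect of 16 in romidepsin's likely and less likely blood-level lists without a scheduled test. Phase IIa toxicity and DLT counts may be under-ascertained by an amount that the documents do not allow one to estimate. Any number of missed patients would rest on an invented incidence; the stopping-probability table shows direction and sensitivity only.

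The conclusion assumes that sites follow the calendar as written, that footnote 3 lists the panel rather than examples from it, and that hypophosphatemia can reach grade 3 under CTCAE v4.0, which the protocol cites but does not reproduce. For the stopping rule to be affected, an unseen event must also be attributed to study drugs, fall within cycles 1-4 and occur in a patient with no other DLT.

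The change is worth making because it is cheap and makes a listed toxicity interpretable within the primary endpoint.

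**What to change.** Add phosphorus to the electrolyte panel in Appendix G, footnote 3, at chemistry time points already in the calendar: at least Days 1 and 8 through cycle 4, cycle 1 Day 15, and end of study. Name it at screening too, so that footnote 3 agrees with Section 8.2. If it is not added, state in the analysis and report that hypophosphatemia was not systematically measured, so that absence of recorded events is not read as absence of the toxicity.

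The cost is one more analyte per draw, with no new visit or draw: 4 × 2 + 1 + 1 = 10 results for a patient who completes four cycles. A few more laboratory adverse events or DLTs may be recorded. This changes what is measured; it proposes no dose rule or treatment criterion.

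Patients treated before the change will lack these values. Hypophosphatemia should therefore be reported with the number of patients actually tested as its denominator.
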